2.4 Combination Restorative Therapy for Erectile Dysfunction

The development of ED therapeutics that focus on neurovascular regeneration and repair strategies are of great importance. A large body of *pre-clinical* work has demonstrated the effect of SWT alone (monotherapy) on angiogenesis and progenitor / stem cell recruitment for ED [2, 3, 8-11]. PRP monotherapy importantly is also supported by well-defined mechanistic insights obtained from rigorously conducted animal studies [12-19]. All the previous studies in humans have evaluated either IIEF scores and / or penile Doppler ultrasound hemodynamic parameters, but there has not been evaluation of the treatment as a combination. The proposed mechanisms of both interventions would

suggest that the combination therapy would act in a synergistic manner, with superiority over monotherapy. Success of our proposed work could fundamentally change the standard of care for ED and substantially improve the quality of life for tens of millions of men.

3. Study Objectives

3.1 Primary Objective:

To investigate and compare the safety of PRP and SWT vs placebo/sham treatment in men with mild-moderate ED.

3.2 Secondary Objective:

To study the treatment efficacy of PRP and SWT treatment vs placebo/sham treatment in men with mild-moderate ED.

4. Study Endpoints

4.1 Primary Endpoint (safety):

- Incidence of treatment emergent serious adverse events (TE-SAEs) in all patients during the study period. Adverse events will be recorded at every visit. The following contains a list of the anticipated adverse events:
 - Pain
 - Bruising
 - Swelling
 - Edema
 - Allergy
 - Penile Fracture
 - New Penile Curvature

4.2 Secondary Endpoints (efficacy):

- Change in IIEF-EF score from baseline to 3 and 6 months post-therapy compared to control group.
- Percentage of subjects that achieve minimal clinically important difference (MCID) in IIEF-EF from baseline to 3 and 6 months post-therapy compared to control group,
- Percentage of subjects who either decrease or discontinue use of PDE5i after three months post-therapy compared to control group.

4.3 Exploratory Endpoints:

- Differences in Doppler ultrasound parameters (PSV and EDV) from baseline to 6 months post-therapy compared to control group.
- Treatment satisfaction as assessed by EDITS questionnaire in all subjects.
- Changes in IPSS questionnaire between treatment and control group.
- Perceptions of therapeutic allocation between treatment and control group.

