7.4 Withdrawal Criteria

All subjects who either screen fails, is withdrawn from the study, or has completed all visits should be de-enrolled from the research database within 2 business days, in accordance with university policies (or respective institutional policy).

Subjects may be withdrawn from the study for any of the following reasons:

- a) A subject does not meet the eligibility criteria (the subject will be considered a screen failure).
- b) A subject withdraws consent.
- c) If a new treatment for erectile dysfunction is made available during the study duration, the investigator will inform the patient at a follow-up visit, and be offered withdrawal to utilize new treatment.
- d) A subject expires during protocol participation from causes other than the study treatment (not due to adverse events).
- e) At the discretion of the principal investigator for issues of non-compliance, or other behavioral factors.

8. Procedures Involved

60 men with Erectile Dysfunction (ED) of organic origin, that meet all of the inclusion and none of the exclusion criteria, will be randomized to receive either PRP+SWT, or placebo/sham in a 1:1 double-blinded fashion.

- a) Group A (30 subjects): Autologous PRP injection + SWT therapy. All subjects in this group will receive 2 sessions of autologous PRP penile injection with 30 ± 7 day treatment interval. 5mL of PRP will be injected at each session. Additionally, patients will receive a total of 3600 shocks over a five-week period, starting at initial PRP injection.
- b) Group B (30 subjects): Placebo (Normal Saline) + SHAM. All subjects in this group will receive 2 sessions of normal saline penile injection with 30 ± 7 day treatment interval. 5mL of normal saline will be injected at each session. Additionally, patients will receive SHAM treatment over a five-week period, starting at initial placebo injection.

8.1 Schedule of Events:

The events table for the conduct of this study is shown below:

Table 1:

Schedule of Events		Screening	Treatment					Follow Up	
Time Point		0-30 days before randomization	Week 1	Week 2	Week 3	Week 4	Week 5	Month 3	Month 6
Event			Day 0	Day 7 \pm 2	Day 14 \pm 2	Day 21 \pm 2	Day 28 \pm 2	Day 90 \pm 14	Day 180 \pm 14
Informed Consent		X							
Demographics		X							
Medical History		X							
Physical Exam		X							
Doppler Ultrasound		X							X
Questionnaires	IIEF	X						X	X
	EDITS							X	X
	VAS		X	X	X	X	X		
	IPSS	X							X
	SGA								X
Laboratory Tests		X							

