8.2 Description of Study Procedures

- 8.2.1 *Informed Consent:*** Refer to Section 7.3 for details regarding the informed consent process. Study procedures will be completed only after participants have signed the informed consent documentation.
- 8.2.2 *Demographics:*** Demographic characteristics will be recorded including: date of birth, gender, marital status, race and ethnicity.
- 8.2.3 *Medical History:*** Assessment of current and past medical, surgical, and social history will be conducted.
- 8.2.4 *Physical Examination:*** Genitourinary/Reproductive system physical exam will be performed.
- 8.2.5 *Phone Call:*** Participants will be contacted by telephone to assess safety outcomes during long term follow up.
- 8.2.6 *Doppler Ultrasound:*** Penile Doppler ultrasound will be performed as standard of care for the management of erectile dysfunction. Results from within the past 12 months can be extracted from the medical record for use in this study.
- 8.2.7 *International Index of Erectile Function (IIEF) Questionnaire:*** This validated 15-item self-evaluation scale provides pre and post treatment clinic evaluations of erectile function, orgasmic function, sexual desire, satisfaction in sexual intercourse and general satisfaction. If the subject has completed the IIEF questionnaire within the past 6 months, those results may be requested and used for the purpose of this research study. Questionnaires will be completed prior to therapy at injection visits.
- 8.2.8 *Erectile Dysfunction Inventory of Treatment Satisfaction (EDITS) Questionnaire:*** This is a psychometrically sound questionnaire used to assess satisfaction with medical treatment modalities for erectile dysfunction.
- 8.2.9 *Visual Analogue Pain Scale (VAS):*** The visual analog scale (VAS) is a validated, subjective measure for acute and chronic pain. Scores are recorded by making a handwritten mark on a line that represents a continuum between “no pain” and “worst pain”.
- 8.2.10 *International Prostate Symptom Score (IPSS):*** This eight-question screening tool used to track symptoms of benign prostatic hyperplasia (BPH)
- 8.2.11 *Subject Global Assessment (SGA):*** In this single-question survey, subjects will be asked which treatment arm they believe that they had received (placebo/sham or active therapy).
- 8.2.12 *Randomization:*** Refer to Section 9.3 for details about randomization plan

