8.3 Description of Study Visits

8.3.1 Screening Visit

Visit 1 (0 – 28 days before therapy): The basic work-up will take place, including medical and sexual history, as well as necessary lab tests (testosterone, prolactin, hematology, chemistry), if not available during the last 12 months prior to screening. Subjects will complete the IIEF questionnaire. We will ensure that patients have 4 attempts for intercourse. Screening visit can occur on same day as first injection + SWT/SHAM. Refer to table 1 for procedures to be performed at the Screening visit.

8.3.2 Treatment Visits: Week 0 – Week 4

Upon evaluation of eligibility, subjects will be randomized to one of the two parallel study groups using an online program, and initiate treatment on the same day.

There will be 5 treatment visits for all groups, each occurring at weekly intervals (± 2 days), for a total duration of five weeks. Subjects will complete a Visual Analogue Scale (VAS) pain score after the end of each treatment. Refer to table 1 for all procedures to be performed at the treatment visits.

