8.3.3 Follow Up Visits: Months 3 and 6 Post-Treatment

Follow up visits will occur within 90 ± 14 days (Month 3) and 180 ± 14 days (Month 6) days after final treatment visit. Refer to table 1 for procedures to be performed at the follow up visits visit.

9. Investigational Product

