9.3 Randomization

On Day 0, participants who remain eligible for the trial will be randomized to one of two groups in a 1:1 ratio. The randomization sequence will be computer generated by the study coordinating team.

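### Baseline Doppler may be a routine scan up to 12 months old: the between-arm PSV/EDV comparison stays unbiased but loses precision, and within-arm change cannot be read as treatment response

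*Combined protocol and SAP*

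**What the plan says.** Section 4.3 lists as exploratory: "Differences in Doppler ultrasound parameters (PSV and EDV) from baseline to 6 months post-therapy compared to control group". Table 1 (section 8.1) places Doppler at two points only: screening, headed "0-30 days before randomization", and Month 6.

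Section 8.2.6 loosens this. It says "Penile Doppler ultrasound will be performed as standard of care for the management of erectile dysfunction" and then "Results from within the past 12 months can be extracted from the medical record for use in this study". It does not say from which date the 12 months run back, and it does not limit the allowance to the baseline scan. It gives no standard for device, stimulation, operator or reading, and does not ask for scan date or method to be recorded.

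Section 8.3.1 adds "Screening visit can occur on same day as first injection + SWT/SHAM", so a screening scan may fall on Day 0. Month 6 has two anchors: Table 1 counts 180 ± 14 days in columns that start at Day 0, while section 8.3.3 has "180 ± 14 days (Month 6) days after final treatment visit".

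Section 14.1 analyses continuous data by repeated-measures ANOVA or t-test, with no covariate for scan age.

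**The concern.** The endpoint is a change from baseline, yet the plan lets baseline be a scan taken on Day 0 in one man and a year-old chart scan in another. Two things follow.

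First, within an arm, change from an old scan contains the course of the disease over that time as well as any effect of treatment. It may also contain a change in medication. Section 6 describes all men as regular PDE5i users, and section 8.2.14 has them stop PDE5i during the study, so an older scan may predate stopping.

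Second, an older scan is likely to correlate less with the Month 6 value, which inflates the variance of the change score in a trial of 30 men per arm.

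PSV and EDV are the only haemodynamic measures among the efficacy endpoints, and so a useful check on the questionnaire results.

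**Working it through.** The plan states no figure for this interval and gives no variability for PSV or EDV, so there is nothing to reproduce. The intervals below come from the plan's windows. The precision figures rest on assumed correlations.

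**1. Interval from baseline scan to Month 6**

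Inputs: screening 0 to 30 days before randomization (Table 1); last treatment visit Day 28 ± 2, so Day 26 to 30 (Table 1); Month 6 at 180 ± 14, so 166 to 194 days (Table 1 and 8.3.3); chart allowance 12 months, taken as 365 days before screening (8.2.6).

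| Baseline rule | Month 6 from Day 0 (Table 1) | Month 6 from final treatment visit (8.3.3) |
|---|---|---|
| Screening-window scan | 0 + 166 = 166 to 30 + 194 = 224 days | 26 + 166 = 192 to 30 + 30 + 194 = 254 days |
| Chart scan allowed | 166 to 365 + 30 + 194 = 589 days | 192 to 365 + 30 + 30 + 194 = 619 days |

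Longest over shortest is 589/166 = 3.5 or 619/192 = 3.2 with the allowance, against 224/166 = 1.3 or 254/192 = 1.3 without it. If the 12 months run back from Day 0 instead, the maxima fall by 30 days, to 559 and 589. Section 8.3.1 gives a 28-day screening window; using it lowers the maxima that include the screening window by 2 days.

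**2. Bias between arms**

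Randomization is on Day 0 (section 9.3). A scan used as baseline precedes it, and the same rule applies to both arms, so scan age and method are balanced in expectation. A simulation illustrates this with 30 per arm and 20,000 runs. Its assumptions were a correlation of 0.7 for a fresh scan falling linearly to 0.4 at 12 months, drift of −0.5 SD per year of scan age, and scan ages uniform over 0 to 12 months.

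- Control-arm change with no treatment effect: 0.00 SD with fresh baselines, −0.25 SD with mixed ages.
- Between-arm difference: 0.00 for a true 0 and 0.50 for a true 0.5 SD. Type I error stayed at 0.05.
- Standard error of the difference: 0.20 SD rising to 0.25 SD. Power for a 0.5 SD effect fell from 69% to 51%.

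**3. Size of the precision loss**

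With equal variances at both times, SD of change = SD × √(2(1 − r)), where r is the baseline/Month 6 correlation. The 95% half-width for the between-arm difference is about 1.96 × √(2/30) = 0.506 times that.

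- r = 0.7: √0.6 = 0.775 SD; half-width 0.39 SD.
- r = 0.6 in every man: √0.8 = 0.894 SD, a rise of 15%; half-width 0.45 SD.
- r = 0.4 in every man: √1.2 = 1.095 SD, a rise of 41%; half-width 0.55 SD.
- Half the men at 0.7 and half at 0.4: √((0.6 + 1.2)/2) = 0.949 SD, a rise of about 22%; half-width 0.48 SD.

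Comparing Month 6 values with no baseline at all gives 0.51 SD. So once r falls below 0.5, subtracting the baseline is worse than ignoring it.

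**4. Alternatives for men with only a chart scan**

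- Excluding them: if that removes half, 15 remain per arm, and at r = 0.7 the half-width is 1.96 × √(2/15) × 0.775 = 0.55 SD. That is no better than the worst case above.
- Adjusting Month 6 for baseline: residual SD is about SD × √(1 − r²). At r = 0.4 this is √0.84 = 0.917 SD, half-width 0.506 × 0.917 = 0.46 SD, against 0.55 for raw change, and every man is kept.

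**The case against.** The strongest reply is that the endpoint is defined against control. A reader might infer from the old baselines that the PSV/EDV result as a whole cannot reflect treatment. The documents do not support that: allocation follows the baseline scan and the allowance is common to both arms, so the randomized contrast is still a fair estimate of the treatment effect. What remains is lost precision and chance imbalance. This part of the reply stands.

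It is also fair that the loss may be small. The plan does not say how many men would use a chart scan, the correlations are assumptions, and the 41% needs every baseline to be old.

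Two further readings go beyond the text. One is that the chart scans come from outside institutions or other machines. Section 8.2.6 says only that they come from the medical record, and section 16 names UHealth and JHS. Differing methods are possible because no standard is set, but they are not documented. The other is a single range of about 5 to 20 months. That joins the shortest interval under one Month 6 anchor to the longest under the other, and neither reading alone gives both ends.

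Finally, Doppler is exploratory in a Phase I/II pilot. The primary and secondary endpoints and the sample size do not depend on it.

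None of this rescues within-arm change, and nothing in section 14.1 recovers the lost precision.

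**Conclusion.** The concern holds in a limited form. Section 8.2.6 undercuts the screening-window baseline in Table 1 and lets the baseline-to-Month-6 interval vary about 3.2- to 3.5-fold between men, against about 1.3-fold with screening-window scans. Within-arm change in PSV or EDV then cannot be read as treatment response. The between-arm comparison remains valid but is less precise by an amount the documents do not determine: 15% to 41% more SD of change if all baselines are old, and about 22% if half are old under the larger drop in correlation. These figures assume r = 0.7 for a recent scan, 0.6 or 0.4 for an old one, equal variances, and 30 men per arm. They omit any extra scatter from drift with scan age. This is an inexpensive improvement to an exploratory endpoint and does not threaten the trial's main results.

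**What to change.** In section 8.2.6, state that for the section 4.3 endpoint:

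- the baseline is the Table 1 screening-window scan, acquired by the same written method as the Month 6 scan;
- the 12-month allowance cannot supply the Month 6 scan;
- where only a chart scan exists, the man stays in the analysis, and the date and method of that scan are recorded.

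In section 14.1, compare Month 6 PSV and EDV between arms by ANCOVA, adjusted for baseline value and scan age, in place of raw change. Say that within-arm change will not be interpreted. Reconcile the Month 6 anchor between Table 1 and section 8.3.3.

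The cost is that some men with a recent clinical scan repeat one, although Table 1 already schedules it, plus two recorded items and slightly more analysis work.

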5.1 Additional Study Sites

No additional study sites.

6. Study Population

60 males with ED of organic origin. All patients will be regular PDE5i users/responders. Men with ED will be evaluated by IIEF-EF domain and eligible patients will be randomized to one of 2 treatment groups with an equal allocation ratio (1:1). Participants who do not meet eligibility criteria will be considered a screen failure and will not receive the study therapy.

6.1 Inclusion criteria:

In order to participate in this study, a patient must:

- 1) Be Male
- 2) Be 30 to 80 years of age (inclusive).
- 3) Be able to provide written informed consent.
- 4) Have a diagnosis of mild to moderate ED (12-21) or mild ED (22-25) based on IIEF-EF questionnaire score.
- 5) Be in a stable heterosexual relationship, and have a minimum of 2 sexual attempts per month for at least one month prior to enrollment..
- 6) Agree to comply with all study related tests/procedures.

6.2 Exclusion criteria:

In order to participate in this study, a patient must not have any of the following:

- 1) Previous penile surgery of any kind (except circumcision and condyloma removal), such as penile lengthening, penile cancer surgery, penile plication, grafting.
- 2) Previous history of priapism, penile fracture, Peyronie's Disease, or penile curvature that negatively influences sexual activity,
- 3) Abnormal morning serum testosterone level defined as a value lower than 300 ng/dL ($\pm 5\%$).
- 4) Psychogenic ED as determined by study investigator.
- 5) Patients using ICI for management of ED
- 6) Patients with generalized polyneuropathy, neurological conditions, or psychiatric disease (such as bipolar disorder or depression).

- 7) Have a serious comorbid illness or condition that, in the opinion of the investigator, may compromise the safety or compliance of the subject or preclude successful completion of the study.
- 8) History of consistent treatment failure with PDE5 inhibitors for therapy of ED.
- 9) Poorly controlled diabetes as indicated by Hemoglobin a1c > 9%.
- 10) Use of antiplatelet medication

7. Identification and Enrollment of Subjects

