- 8.2.13 *PRP/Placebo Injection:*** Approximately 120mL of blood will be collected from participants for preparation of investigational product. Refer to Section 9.2 for description of IP preparation and administration.

8.2.14 Concomitant Medications: Review of current use of prescription and over the counter (OTC) medications. Participants must discontinue use of PDE5i medications throughout the duration of the study.

8.2.15 Review Adverse Events: Refer to Section 12 for description and reporting of adverse and serious adverse events.

8.2.16 SWT/Sham Treatment: In the treatment group, patients randomized will receive 5 weekly sessions, in which 720 shocks of treatment energy will be applied in every session to each treated region (left and right corpora cavernosa and crura). In the sham group, patients will have the same number of sessions, and the machine will be set to deliver 720 shock treatments, but the machine will not fire shockwaves.

8.2.17 Laboratory Testing: Hematology, chemistry, hemoglobin A1C, and serum testosterone lab test results will be collected at screening. If any standard of care labs testing have been performed within 12 months of the date of the screening visit, those results may be used for the purpose of this study.

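### The baseline IIEF-EF may be an on-PDE5i score up to 6 months old, and the PDE5i condition at follow-up is contradictory, so change and MCID response may compare unlike conditions

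*Combined protocol and SAP*

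**What the plan says.** All references are to the combined protocol and SAP.

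- **Source of the score.** Section 8.2.7: "If the subject has completed the IIEF questionnaire within the past 6 months, those results may be requested and used". No PDE5i condition is attached. The same section adds: "Questionnaires will be completed prior to therapy at injection visits".
- **Schedule.** Table 1 in section 8.1 lists the IIEF at screening, Month 3 and Month 6 only. Section 8.3.1 has subjects complete it at screening and also states: "Screening visit can occur on same day as first injection + SWT/SHAM".
- **PDE5i at entry.** Section 6: "All patients will be regular PDE5i users/responders".
- **PDE5i on study.** Section 8.2.14: "Participants must discontinue use of PDE5i medications throughout the duration of the study". No interval between stopping and the baseline IIEF is given.
- **Endpoints that use baseline.** Section 4.2: "Change in IIEF-EF score from baseline to 3 and 6 months post-therapy compared to control group" and "Percentage of subjects that achieve minimal clinically important difference (MCID) in IIEF-EF from baseline to 3 and 6 months post-therapy compared to control group".
- **Endpoint that presumes PDE5i use.** Section 4.2 also lists: "Percentage of subjects who either decrease or discontinue use of PDE5i after three months post-therapy compared to control group".

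No section says which IIEF score is the baseline.

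**The concern.** A chart score predates consent, and so predates the study's PDE5i stop. A fresh score taken at a screening visit on the first treatment day need not follow any off-drug period either. In men who all use PDE5i regularly, either score may describe function with the drug. If 8.2.14 is followed, the Month 3 and Month 6 scores describe function without it. Each man's change would then be the treatment effect minus whatever he lost by stopping PDE5i, and the age of the baseline would vary between men.

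The IIEF-EF score does three jobs: it decides eligibility (12 to 25, section 6.1), it sets the severity class and so the MCID threshold (2 or 5 points, section 14.2), and it is the value subtracted. A baseline taken under a different condition can distort all three. MCID response is also the quantity on which section 14.2 sizes the trial.

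**Working it through.** **1. The plan's own figure.** Section 14.2 gives 15% vs 50% meeting MCID, z values 1.96 and 0.84, and P = 0.25:

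2 × (1.96 + 0.84)² × 0.25 × 0.75 / 0.35² = 2.94 / 0.1225 = 24.0 per arm; 24 / (1 − 0.20) = 30 per arm, 60 in total.

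This reproduces. At 24 per arm, exact power of Fisher's test (the test named in 14.1, two-sided 0.05) for 15% vs 50% is 67%. The gap between 67% and the planned 80% is a separate matter; 67% is the starting value here.

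**2. The passages side by side.**

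| Time | What the text allows | PDE5i condition |
|---|---|---|
| Chart IIEF, up to 6 months old (8.2.7) | may be used | not stated; regular users (6), before the study's stop |
| Screening IIEF, possibly the first-injection day (8.3.1) | completed at visit | not stated; no interval required |
| Months 3 and 6 | completed at visit | off, by 8.2.14; use implied, by the third endpoint in 4.2 |

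If 8.2.14 were followed by everyone, every man in both arms would have discontinued, and the PDE5i endpoint could not separate the arms. The two passages cannot both describe follow-up.

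**3. Mean change.** Assumed inputs: active gain 4.14 (the mean quoted in 14.2 from a small PRP study), control gain 0.5 (assumed), SD of change 5 (assumed), 24 per arm.

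- Difference: 4.14 − 0.5 = 3.64 points. Two-sided t-test power is 69%.
- A constant loss L in both arms gives (4.14 − L) − (0.5 − L) = 3.64. Power stays at 69% whatever L is.
- If half the men in each arm lose 3 points and half lose none, the added variance is 0.25 × 3² = 2.25. The SD becomes √(25 + 2.25) = 5.22, and power is 66%.

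**4. MCID response.** Treat change as normal, placed so that 15% and 50% meet MCID with no loss (thresholds 1.036 and 0 SD above the arm mean). A loss of L points in both arms gives control rate 1 − Φ(1.036 + L/SD) and active rate 1 − Φ(L/SD). With an assumed SD of 5:

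| Loss (points) | Control | Active | Difference | Fisher power, 24 per arm |
|---|---|---|---|---|
| 0 | 15.0% | 50.0% | 35 points | 67% |
| 1 | 10.8% | 42.1% | 31 | 62% |
| 2 | 7.5% | 34.5% | 27 | 56% |
| 3 | 5.1% | 27.4% | 22 | 47% |
| 4 | 3.3% | 21.2% | 18 | 36% |

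Range over the assumed SD, from 4 to 8: a 2-point loss gives power of 52% to 61%, and a 4-point loss gives 22% to 52%.

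**5. False positives.** With no treatment effect and the same loss in both arms, the two response rates are equal. Fisher's test at 24 per arm then favours active with probability 1.2% at a common rate of 15% and 0.3% at 6%, both below the nominal 2.5%.

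**6. Eligibility and MCID class.** The documents give no distribution of baseline scores and no size for the PDE5i effect, so the number of men who could be misplaced cannot be computed.

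**The case against.** - **Baseline drug status is an inference.** Regular use at entry does not show how any particular IIEF was answered. A reader might conclude that baseline is an on-drug score. The documents support only that it may be.
- **The chart allowance is permissive.** Section 8.3.1 has men complete an IIEF at screening, and 7.1 uses IIEF-EF on file for pre-screening, so the allowance may have been meant for that. The sentence about injection visits can be read as an order-of-events rule when screening falls on Day 0. This is an ambiguity to settle, not a fixed rule that baseline comes from the chart. But the text does permit it.
- **Follow-up may not be off drug.** A reader might take 8.2.14 as settling this. The PDE5i endpoint in 4.2 points the other way. If men use PDE5i during follow-up, the loss could shrink or vanish. If use resumes unequally between arms, the between-arm contrast would be affected too. The direction is therefore not certain.
- **Both arms are affected alike.** Every IIEF endpoint is a comparison with control. A reader might infer a biased treatment effect or a spurious positive. A loss common to both arms supports neither: the mean difference is protected in expectation, and t-test power on change barely moves.
- **Rank of the endpoint.** Section 4 makes safety primary and IIEF secondary in a Phase I/II pilot, although the synopsis states efficacy as the primary objective.

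All five stand as limits. None removes the gap: the plan defines no baseline score and no PDE5i condition for it.

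**Conclusion.** The concern holds in a conditional form and should be fixed. As written, the plan can be followed to the letter and still produce change and MCID scores that compare different PDE5i conditions, with baselines of different ages.

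The size depends on the endpoint. For mean change it is small: 69% power under any constant loss, 66% if half the men lose 3 points. For MCID response it is material if the loss is real: Fisher power falls from 67% to 56% for a 2-point loss and to 36% for a 4-point loss. These figures rest on an assumed loss, an assumed SD of 5 and a normal model for change. The mean-change figures also rest on an assumed control gain of 0.5. Misplacement in the eligibility band or MCID class is possible but cannot be quantified. The case is one of blurred response rates and lost power on the MCID endpoint, not of bias towards active treatment.

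**What to change.** 1. In 8.2.7, limit the chart IIEF to pre-screening.
2. Define one IIEF, completed before the first injection (at screening or Day 0), as the baseline for every man, and make 8.1 and 8.2.7 agree on it.
3. Record PDE5i use over the period that each IIEF covers, at baseline and at Months 3 and 6.
4. Reconcile sections 4.2, 6, 8.2.14 and 8.3.1 on PDE5i use at baseline and follow-up so that the two are comparable. How this is done is for the sponsor to set.

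The cost is one short questionnaire for some men, one extra data item per IIEF and edits to the schedule. Depending on how the passages are reconciled, fewer men may be able to screen and start treatment on the same day. The change has to come before treatment starts, because a baseline cannot be collected again afterwards.
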